#### SLIPS assessment inclusion

Consenting patients will also undergo SLIPS assessment if they fulfil the following additional inclusion criteria:

- 1) The right foot can be accommodated by a size 8-11 shoe.
- 2) Weight < 100kg

Patients will be ineligible if they meet any of the following exclusion criteria:

- 1) Those who are unable to mobilise independently 150m, without the use of walking aids and thus unable to complete the walking assessments
- 2) Toe pressure < 40mmHg
- 3) Presence of a foot deformity
- 4) Previous ipsilateral minor amputation
- 5) Previous contralateral major amputation

## **9. Matching**

Matching of DFU and Low risk groups will not be performed.

Rationale:

In a study by Yavuz et al., (2014), investigating PSS in neuropathic and non-neuropathic patients with diabetes, neither BMI nor age accounted for a significant proportion of the variance of shear between groups.

Furthermore, the effect of age, BMI, gender and walking speed can be adjusted for if appropriate in the analysis.

To ensure equal group sizes for SLIPS assessment, the proportion of patients per group will be monitored and selective sampling according to shoe size and weight will be performed and recruitment adjusted as appropriate.

## **10. Recruitment**

### **10.1 Recruitment setting**

Patients within the DFU group will be recruited from secondary care from the LTHT Diabetes Limb Salvage Service clinics. The service is run by podiatrists, diabetologists, vascular surgeons and orthotists specialising in care of the diabetic foot. Patients within the Low risk group will be recruited through the Leeds Community Healthcare NHS Trust (LCH) podiatry service which has diabetic foot protection clinics with podiatry led care.

### **10.2 Recruitment process**

All patients with diabetes and a recently healed plantar DFU seen within the Diabetes Limb Salvage Service clinic will be considered as potentially eligible for this study. Where indicated by the attending clinical team and after agreeing to further information, patients will receive a full verbal explanation of the study and a Patient Information Leaflet (PIL) by either the attending clinical team or a member of the clinical research team at a time convenient to the patient during their routine clinic visit. Consenting patients will undergo an eligibility

assessment within their routine clinic appointment. An appointment will then be booked to attend the walking assessments. All data will be collected within a single visit.

The Low risk group will be recruited using the Leeds Community Healthcare podiatry service. The service will review their caseload and identify potentially eligible patients who will be sent a letter and the PIL. The letter will include a brief introduction to the study and patients will be invited to contact the research team by return of the form, email or via telephone if they are interested in participating. Assenting patients will then undergo an eligibility assessment via telephone and be invited to attend a research clinic visit for consent and study assessments. Community clinics may also be attended by the clinical research team to enable immediate referral of patients identified by the attending clinical team; all low risk patients will receive a full verbal explanation of the study and a Patient Information Leaflet (PIL) by a member of the clinical research team at a time convenient to the patient during their routine clinic visit. Consenting patients will undergo an eligibility assessment within their routine clinic appointment. An appointment will then be booked to attend the walking assessments. All data will be collected within a single visit. ;

## **10.3 Screening**

A log will be kept of all patients who have had an eligibility assessment but have not been recruited for the study. Documented reasons for ineligibility or declining participation will be collected and monitored. The following anonymised data will be collected in the log:

- 1) Age
- 2) Gender
- 3) Ethnicity
- 4) Date screened
- 5) Reason not suitable for study OR
- 6) Reason for declining participation

## **10.4 Informed consent and eligibility**

As per the recruitment section, patients will have received a PIL and a full verbal explanation of the study. Patients will have as long as they need to consider participation and will be given the opportunity to discuss the study with family and other healthcare professionals before they are asked whether they would be willing to take part. Patients will also be provided with the contact details of the research fellow where he/she may be able to obtain further information about the study. During the consent process, patients will have the opportunity to ask questions.,

The Chief Investigator (CI) retains overall responsibility for the informed consent of participants and must ensure that any person delegated responsibility to participate in the informed

consent process is duly authorised, trained and competent to participate according to the ethically approved protocol, principles of Good Clinical Practice (GCP) and Declaration of Helsinki 1996.

The informed consent process will be undertaken by the clinical research team or registered healthcare professional who is GCP trained.

The CI takes responsibility for ensuring that all vulnerable subjects are protected and participate voluntarily in an environment free from coercion or undue influence.

Informed consent must be obtained prior to the patient undergoing procedures that are specifically for the purposes of the study (including the collection of identifiable participant data). The right of a participant to refuse participation without giving reasons must be respected. The participant must remain free to withdraw at any time from the study without giving reasons and without prejudicing his/her further treatment and will be provided with a contact point where he/she may obtain further information about the study.

Should the participant be capable of giving consent but physically unable to complete the written aspects of the consent form, witnessed consent should be obtained. An appropriate witness would be a family member or friend of the patient, or another member of the participant's healthcare team who is not directly involved in the research study.

A record of the consent process detailing the date of consent and those present will be detailed in the patients' healthcare records. The original consent form will be filed securely by the clinical research team in a locked filing cabinet in a locked room at the Leeds Vascular Institute and a second copy uploaded to the electronic patient record (as per local practice).

## **11. Data collection**

Following consent within the routine clinic appointment, patients within the DFU group will be invited will be invited to a research visit for the baseline clinical assessment and the strain, PSS and pressure assessment. Consent, baseline assessments and strain, PSS and pressure assessments for the Low risk group will be performed in one visit. All assessments are expected to be performed within a one-hour visit.

### **11.1 Clinical Characteristics**

Following informed consent, demographics and clinical characteristics for each patient will be documented. A standardised proforma will be used to collect clinical characteristic data. History, examination and review of the medical records will be performed to collect information on: Age, sex, weight, height, duration of diabetes, presence of DPN, smoking status, duration of ulceration, time since ulceration, toe pressure, HbA1c (within the last 6 months), pre-ulcerative lesion at entry, presence and type of foot deformity.

Presence of co-morbidities including presence of chronic kidney disease, defined as an eGFR <60 for three months; heart failure, based upon clinic records. These characteristics are based upon reporting standards guidelines.[15]

Definitions:

Diabetic Peripheral Neuropathy – Diagnosed using 10g monofilament test. Methodology will be as described in the International Working Group for the Diabetic Foot guidelines on the prevention and management of diabetic foot disease.[5]

Pre-ulcerative lesion – Skin fissure, intra-cutaneous/subcutaneous haemorrhage or blister (IWGDF definition of pre-ulcerative lesion).[13]

## 11.2 Pressure and strain measurement

To reduce measurement bias, the order of tests performed will be randomised using the Latin square method.

## 11.3 STAMP

For the DFU group, the foot with the recently healed DFU will be analysed. For the Low risk group the right foot will be selected. Evidence suggests that there is no difference in vertical, or antero-posterior ground reaction force between dominant or non-dominant limb, therefore no bias should be introduced.[16]

To capture strain data an insole is created using plasticine and inserted into a trial shoe, a standard sock will be worn before donning the trial shoe the patient then undertakes a walking assessment.

The procedure is as follows:

A pseudo-random pattern will be marked onto a plasticine sheet of uniform thickness. An image of this will be taken prior to placing this onto the in-sole of a trial shoe. Each participant will be provided with a pair of disposable socks and be asked to wear the provided trial shoes. Participants will be asked to take 10 **steps** forward and then turn around to walk back to the initial position at their natural speed and step length before removing the STAMP insole. Three

repeats of this activity will be performed. Walking speed will also be recorded using an accelerometer.

An image will be taken of the pattern following the walking assessment. Pre- and post-walking assessment images will be compared using the software GOM Correlate, and analysis performed with the MATLAB analysis package.

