### **7.1 Blinding**

To reduce the risk of measurement bias during data collection, the order of tests will be randomised using the Latin square method.

To reduce the risk of observer bias, data will be analysed in batches, with the assessor blinded to patient group.

A subsample of 10% of the patients will undergo analysis by a second assessor, also blinded to patient group and level of agreement analysed.

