## **8. Eligibility**

### **8.1 DFU group**

Inclusion criteria

All patients with diabetes who have a recently healed plantar DFU will be identified by the clinicians within the Diabetes Limb Salvage Service and assenting patients will be assessed for eligibility by the research team. Patients will undergo STAMP and Pedar assessment if they fulfil the following inclusion criteria:

- 1)  $\geq 18$  years of age
- 2) A diagnosis of diabetes mellitus
- 3) A diagnosis of diabetic peripheral neuropathy (DPN)
- 4) Recently healed plantar DFU (healed within the last 3 months)
- 5) Provide informed written/witnessed verbal consent to participate

Exclusion criteria

Patients will be ineligible if they meet the any of the following exclusion criteria:

- 1) Those who are unable to mobilise independently 150m, without the use of walking aids and thus unable to complete the walking assessment
- 2) Previous ipsilateral minor amputation
- 3) Previous ipsilateral surgical offloading procedure
- 4) Previous contralateral major amputation
- 5) Ipsilateral toe pressure <40mmHg
- 6) Previous open or endovascular ipsilateral revascularisation

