#### SLIPS assessment inclusion criteria

The SLIPS insole has been designed to measure the plantar load of the right foot, and due to its size, can only be accommodated by a size 8-11 shoe. The insole is also only able to accommodate patients weighing <100kg. Therefore, in addition to the above criteria, patients will undergo SLIPS assessment if they fulfil the following additional inclusion criteria:

- 1) Recently healed plantar DFU located on the right foot
- 2) The right foot can be accommodated in a size 8-11 shoe
- 3) Weight <100kg

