## **11.4 Pedar**

To capture pressure data the patient will undertake a walking assessment using the Pedar system.

The procedure is as follows:

The appropriately sized Pedar insole will be placed into the provided trial shoe the side of recently healed ulcer for the DFU group. The insole will be placed into the right shoe of the Low risk group. Each patient will be asked to walk 10 **metres** forward and then turn and walk back to the initial position at their natural speed and step length. Three repeats of this activity will be conducted.

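### Foot side discloses group: Low risk patients are always measured on the right foot, so a left-foot STAMP or Pedar file can only come from a DFU patient, and the assessor blinding in Section 7.1 does not hold as written

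*Combined protocol and SAP*

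**What the plan says.** Section 7.1 names observer bias as a risk and gives blinding as the safeguard: "data will be analysed in batches, with the assessor blinded to patient group". It adds a reliability check: "A subsample of 10% of the patients will undergo analysis by a second assessor, also blinded to patient group". No exception is stated for either assessor.

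Section 11.3 fixes the foot measured by STAMP. In one group the side follows the ulcer: "For the DFU group, the foot with the recently healed DFU will be analysed". In the other it is constant: "For the Low risk group the right foot will be selected". Section 11.4 does the same for Pedar. The insole goes on the ulcer side in the DFU group, and "The insole will be placed into the right shoe of the Low risk group".

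The general DFU inclusion criteria in Section 8.1 ask for a plantar ulcer healed within three months and set no foot side. A right-foot ulcer is required only for the additional SLIPS assessment, because "The SLIPS insole has been designed to measure the plantar load of the right foot". Left-foot ulcers are therefore expected among the patients who have STAMP and Pedar only.

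Section 14 makes peak plantar strain from STAMP one of the two primary measures. Pedar pressure and PTI are secondary.

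**The concern.** Side is fixed in one group and free in the other, so it carries information about group. An assessor who sees a left foot knows that the patient had an ulcer. An assessor who sees a right foot knows that Low risk is more likely than not.

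The assessor will probably see the side. The regional analysis places ten regions, including the hallux and the first to fifth metatarsal heads, and these cannot be located without knowing which edge of the foot is medial. No section describes mirroring images, removing side labels or balancing side between groups.

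Section 11.3 defends the right-foot choice by citing similar ground reaction forces in dominant and non-dominant limbs. That answers a biomechanical question and does not address disclosure of group.

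At stake is the credibility of a blinded reading of a primary measure obtained by a method that Section 4 calls untested. The 10% agreement check gives no protection here: two assessors who see the same cue can agree with each other and share the same bias.

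**Working it through.** **Inputs from the plan**

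- Group size: 28 per group, 56 in total (Section 15).
- STAMP and Pedar foot: ulcer side in the DFU group, always right in the Low risk group (Sections 11.3 and 11.4).
- Second assessor: 10% of patients (Section 7.1).

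**Input assumed**

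- L, the share of DFU patients measured on the left foot. The documents do not give it. I use 0.3, 0.5 and 0.7, and also show the limits 0 and 1.

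**The plan's own figure.** With a difference of 4, an SD of 6, 80% power and the 90% significance level read as two-sided alpha 0.10, n = 2 × (1.645 + 0.842)² × 6² / 4² = 27.8, so 28 per group. The figure reproduces. It is not in dispute and serves here only as the group size.

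**Formulas, with equal groups of 28**

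- P(DFU | left file) = 1 for any L above 0.
- Share of files disclosed with certainty = 28L / 56.
- P(Low risk | right file) = 28 / (56 − 28L).
- Accuracy of guessing group from side alone (left = DFU, right = Low risk) = (28 + 28L) / 56. Without any cue it is 50%.

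| L (assumed) | Files disclosed | P(Low risk given right) | P(DFU given right) | Guess correct |
|---|---|---|---|---|
| 0.3 | 8.4/56 = 15% | 28/47.6 = 59% | 41% | 36.4/56 = 65% |
| 0.5 | 14/56 = 25% | 28/42 = 67% | 33% | 42/56 = 75% |
| 0.7 | 19.6/56 = 35% | 28/36.4 = 77% | 23% | 47.6/56 = 85% |

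From L = 0 to L = 1 the share disclosed runs from 0% to 50%. It is zero only if no enrolled DFU patient is measured on the left foot.

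**Second assessor.** 10% of 56 is 5.6, taken as 6 patients. Section 7.1 does not say how they are chosen, so a random draw is assumed. With k left-foot DFU patients (28L rounded to 8, 14 or 20), P(at least one left-foot file) = 1 − C(56 − k, 6) / C(56, 6):

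- k = 8: 62%
- k = 14: 84%
- k = 20: 94%

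**SLIPS.** Both groups are measured on the right foot, so side says nothing about group for peak PSS.

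**The case against.** The strongest reply is that disclosure biases a result only if a person can move the value. Strain comes from GOM Correlate and MATLAB, and the regions are placed by a masking algorithm, so little judgement may remain. This stands as a limit on the claim: no bias in strain has been shown, and none can be sized from the documents. It does not rescue the blinding. The plan itself provides for an assessor, for blinding and for an agreement check, which makes sense only if some judgement enters.

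Several narrower points also stand:

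- The need to know side in order to place regions bears mainly on the regional analyses, which are secondary. Pedar outcomes are secondary too.
- Peak PSS, the other primary measure, is untouched.
- The left share is an assumption. Section 9 plans to adjust recruitment to equalise the SLIPS groups. It names shoe size and weight rather than side, but the effect could be fewer left-foot ulcers.
- No agreement check can detect a bias that both assessors share, whatever its source. The subsample figures show only how often the second assessor would meet a disclosed file.
- Mirroring leaves other cues in place. "Presence of a foot deformity" is an exclusion in the Low risk group only, so foot shape or load pattern may still suggest group.

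One objection fails. Section 16 also calculates mean changes in coordinates, and mirroring reverses their medio-lateral sign. But mirroring places left feet on the same medial-lateral axis as right feet, and the original side can be restored once values are locked.

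**Conclusion.** The concern holds. The blinding in Section 7.1 and the foot-selection rules in Sections 11.3 and 11.4 cannot both hold as written once a single DFU patient with a left-foot ulcer is enrolled, and the eligibility criteria allow this. Blinding is broken for left-foot STAMP and Pedar files and weakened, not lost, for right-foot ones.

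The size depends on the unknown left share. At an even split, a quarter of the STAMP files are disclosed, and the possible range is 0% to 50%. This rests on 28 patients per group and on the assessor being able to see the side. The effect on estimated strain is unknown.

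The change should be made. A stated safeguard on a primary measure fails on paper, the repair is cheap, and without it the report could not accurately say that the STAMP analysis was blinded to group.

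**What to change.** Add to Section 7.1:

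- Before analysis, a script mirrors both images of every left-foot STAMP pair, and the sensor map of every left-foot Pedar export, to right-foot orientation.
- All files, from both feet, lose their side labels and receive a neutral code.
- An existing team member who does not assess those files runs the script and holds the key.
- Each batch contains files from both groups, and the second assessor receives the same prepared files.
- Side is restored only after values are locked.

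Mirroring leaves peak magnitudes unchanged. The plan should state as a limitation that only one cue is removed, since deformity is excluded in the Low risk group alone. SLIPS needs no change for foot side.

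The cost is one script and a little extra file handling, with no new patients, measurements or readers, and the sample size stays at 28 per group. The documents do not describe the Pedar export format, so the team should confirm that it can be mirrored before region masking. If it cannot, the plan should say that Pedar analysis is not fully blinded.

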## **11.4 Pedar**

To capture pressure data the patient will undertake a walking assessment using the Pedar system.

The procedure is as follows:

The appropriately sized Pedar insole will be placed into the provided trial shoe the side of recently healed ulcer for the DFU group. The insole will be placed into the right shoe of the Low risk group. Each patient will be asked to walk 10 **metres** forward and then turn and walk back to the initial position at their natural speed and step length. Three repeats of this activity will be conducted.

## **11.5 SLIPS**

To capture PSS data the patient will undertake a walking assessment using the SLIPS insole.

The procedure is as follows:

The sensing insole will be placed inside a commercial shoe (manufactured by Steeper Group, Leeds) for the right foot. A leather/foam insole (with the same size and thickness to the sensing insole) will be put into the shoe for the left foot. Each patient will be provided a pair of disposable socks and be asked to wear the provided shoes.

Patients will be allowed a short period of time to acclimatise to the shoes. Patients will then be asked to walk 10 **metres** forward and then turn around to walk back to the initial position at their natural speed and step length. Three repeats of this activity will be conducted.

## **12. Withdrawal of Consent**

Patients may withdraw consent from the study at any time without explanation. The CI or PI or should make every effort to ensure that the specific wishes of any patient who wishes to withdraw from further involvement in the study are defined and documented using the withdrawal case report form. Patient withdrawal will be classified as follows:

- a) Withdrawal following STAMP walking assessment
- b) Withdrawal following Pedar walking assessment
- c) Withdrawal following SLIPS walking assessment

For a), b) and c) patients will be offered to allow use of data up to the point of withdrawal. Patients can request complete withdrawal of data if it has not been included in an analysis; data utilised in analysis will not be withdrawn.

Patients who wish to discontinue performing the walking assessments will be allowed to at any point. Reasons for this will be explored and patients will be offered to return at another appointment if appropriate. Data that has been collected up to that point will be used in the analysis with the patient's consent.

## **13. Adverse and serious adverse events**

### **13.1 General definitions**

An Adverse Event (AE) is any untoward medical occurrence in a patient or a clinical trial subject which does not necessarily have a causal relationship with the device/procedure.

A Serious Adverse Event (SAE) is an untoward occurrence that:

- Is fatal
- Is life threatening
- Requires hospitalisation or prolongation of existing hospitalisation
- Results in persistent or significant disability
- Consists of a congenital anomaly or birth defect
- Is otherwise considered medically significant by the Investigator

A Related Unexpected Serious Adverse Event (RUSAE) means for an SAE occurring to a research participant in the opinion of the Chief Investigator was:

- 'Related' that is, it resulted from the administration of any of the research procedures, and
- 'Unexpected' that is, the type of event is not listed in the protocol as an expected occurrence.

Medical and scientific judgement must be exercised in deciding whether an event is serious. These characteristics/consequences must be considered at the time of the event and do not refer to an event which hypothetically may have caused one of the above.

